4.4.4. Downloading of electroporation data from CELLECTRA®5P device

Within 48 hours following each treatment with MEDI0457, data should be downloaded from the EP device and the data file that is created should be sent to the Inovio or designee by e mail to [contact]. Instructions on how to download the data are provided separately. Training will be provided.

4.5. Accountability and Disposition

The investigator, or a responsible party designated by the investigator, must maintain a careful record of the inventory and disposition of the agent using the NCI Drug Accountability Record Form (DARF). See the CTEP home page at http://ctep.cancer.gov for the Procedures for Drug Accountability and Storage or to obtain a copy of the DARF. Any deviation or error in use of CELLECTRA®5P device must be reported error reporting form (Appendix C)

The site will account for all investigational study drug dispensed and also for appropriate destruction. Certificates of delivery and destruction must be signed.

5. STUDY PLAN

All study procedures will be performed according to **Table 3**.

Version Number: 1.8 Date: July 26, 2019

Proprietary of MD Anderson Cancer Center

Table 3. Schedule of Study Procedures

	Screening	(Cycle 1		Cyc	ele 2	Cy	cle 3	Cycle 4 ^a	Cycle 5 ^a	EOT ^b	Follow-up ^c
Week of Study	-	1	3	4	7	8	10	12	16	20	-	-
Procedures Day of Week	-28 to -1	1 ±7 days (unless otherwise noted)										
Informed consent	X											
Demographics	X											
Medical histories ^d	X											
Inclusion/exclusion criteria	X	X										
Physical examination ^e	X	Xf	X	X	X	X	X	X	X	X	X	
ECOG performance status	X	X^{f}	X	X	X	X	X	X	X	X	X	
Adverse events assessment	X	X	X	X	X	X	X	X	X	X	X	
Concomitant medications/procedures	X	X	X	X	X	X	X	X	X	X	X	
Disease status ^g	X ^h							Xi		X ^{i,j}	X	X^k
Hepatitis/HIV screening ¹	X											
Vital signs ^m	Xg	Xf	X	X	X	X	X	X	X	X	X	
12-lead ECG	X	Xf				X		X		X ⁿ	X	
HPV typing ^o	X											
Hematology ^p	X	Xf	X	X	X	X	X	X	X	X^q	X	
Serum chemistry ^r	X	Xf	X	X	X	X	X	X	X	X^q	X	
Coagulation testing ^s	X	As clinically indicated.										
Thyroid function testing ^t	X	X^{f}		X		X		X	X	X^q	X	
Urinalysis ^u	X	As clinically indicated.										
Pregnancy test ^v	X^{w}	X ^x		X		X		X	X	X	X	
MEDI0457 administration ^y		X	X		X			X		X		
MEDI0457 post-treatment reaction ^z		X	X		X			X		X		
Download EP data		X	X		X			X		X		
Durvalumab administration ^{aa}				X		X		X	X	X		
Tumor biopsy ^{bb}	X						Xcc				X^{dd}	
Immune Profiling/HPV Serology Research Bloodee		X		X		X	X		$X^{\rm ff}$		X	
Pharmacokinetics/ADA Research Blood ^{gg}				X		X			X^{hh}			
Viral load ⁱⁱ	X			X		X		X	X	X	X	
HBV DNA/Hep BsAg ^{jj}				X		X		X			X	

Version Number: 1.8

Proprietary of MD Anderson Cancer Center Date: July 26, 2019

- ^a Patients can continue on the study until progression or unacceptable toxicity as long as the physician feels the patient is receiving benefit. Cycles 4 and 5 should be repeated to continue this treatment. ^b End of treatment (EOT) is defined as the last visit where the decision is made to discontinue protocol directed treatment.
- ^c A clinic visit is not required for follow-up. Patients who are taken off study due to disease progression or intolerable toxicities will be followed for vital status every 6 months via phone and/or review of medical record.
- ^d Histories include medical history, history of prior cancer treatment, history of procedures
- ^e Complete physical examination during Screening and at the Follow-up visit; targeted physical examination at all other visits.
- f If performed within 3 days prior to Day 1, they do not need to be repeated.
- g The preferred method of disease assessment is CT with contrast. The same method is preferred for all subsequent tumor assessments for the same patient. Patients discontinued from treatment for reasons other than PD will continue disease assessments until confirmed PD or start of subsequent anticancer therapy.
- h Magnetic resonance imaging scan of the brain will be performed only at screening or at each assessment if the patient is neurologically symptomatic during treatment outside of the setting where the patient has known central nervous system metastases.
- ¹ If possible, disease status assessments will be performed on the day prior to scheduled drug administration.
- ^j Disease status assessments will be performed every 8 weeks (± 3 days) (relative to the date of the first MEDI0457 administration) for 1 year, if CR/PR/SD are achieved then disease status assessments should be performed every 12 weeks (± 7 days) until the EOT.
- k If no PD, disease assessment should be performed on Day 90 (± 7 days) after EOT, every 3 months (± 7 days) after Day 90 up to Month 12, and then every 6 months (± 14 days) after Month 12 until the end of study (EOS).
- ¹ Hepatitis screening tests include: HBV-DNA, HCV-Ab, HBsAg, HBcAB, and HBsAb.
- Temperature, respiratory rate, pulse oximetry, blood pressure, HR and weight. Height will be measured only during Screening. See Section 6.5.7 for details.
- ⁿ Every 12 weeks until end of treatment.
- o Historical tissue samples may be used; there is no need for additional samples/test for the HPV 16/18 test to be collected just for this protocol.
- P Hematology panel includes: basophils, eosinophils, hematocrit, hemoglobin, lymphocytes, mean corpuscular hemoglobin, mean corpuscular hemoglobin, concentration, mean corpuscular volume, monocytes, neutrophils, platelet count, red blood cell count, total white cell count. For patients in the HIV(+) cohort, CD4 and CD8 counts will be performed.
- ^q Every 4 weeks for first 12 months and every 3 months thereafter until study discharge.
- Serum Chemistry panel includes: albumin, alkaline phosphatase, ALT, AST, bicarbonate, calcium, chloride, glucose, lactate dehydrogenase, magnesium, potassium, sodium, total bilirubin (if Total bilirubin is $\ge 2x$ ULN [and no evidence of Gilbert's syndrome] then fractionate into direct and indirect bilirubin), total protein, creatinine, creatinine phosphokinase, blood urea nitrogen, uric acid, amylase and lipase. Please note: GGT to be collected at baseline and as clinically indicated.
- ^s Prothrombin time, APTT and INR.
- Free triiodothyronine (T₃) and free thyroxine (T₄) will only be measured if TSH is abnormal. They should also be measured if there is clinical suspicion of an AE related to the endocrine system.
- ^u Urinalysis panel includes: bilirubin, blood, glucose, ketones, pH, protein, specific gravity, and color/appearance.
- ^v Only for women of childbearing potential.
- To include luteinizing hormone and follicle-stimulating hormone only for women of child bearing potential who may be post-menopausal.
- x Patients with a negative serum pregnancy test within 3 days prior to Day 1 do not require a Week 1 Day 1 pregnancy test to be performed.
- y A window of ±3 days for all time points except C1D1. For Cycles 1 and 2, an interval of 7 days must occur between MEDI0457 and durvalumab treatments.
- ² MEDI0457 post-treatment reactions will be assessed 30 to 60 min after study treatment.
- ^{aa} A window of ± 3 days applies to all time points.
- bb Core tumor biopsies will be collected as per **Section 6.6.1**.
- cc ± 3 days. Biopsies at this time point are required until 10 subjects have provided tissue and then are optional for all subsequent subjects.
- dd At time of confirmed disease progression; Optional
- ^{ee} See **Section 6.6.2.1** for HPV Serology Research Blood details.
- ff Week 16 and then every 8 weeks until end of treatment.
- gg See Section 6.6.2.2 for Pharmacokinetics/ADA details.
- hh Week 16 only.
- ii For HIV(+) patients, viral load will be drawn at baseline, every month for the first 3 months, then every 3 months thereafter while on therapy.
- ^{jj} For patients with inactive Hepatitis B (Hep B core Ab(+)/HepB sAg (-)), HBV DNA and Hep BsAg will be monitored every month for the first 3 months, then every 3 months thereafter while on therapy.

Version Number: 1.8 Date: July 26, 2019 Proprietary of MD Anderson Cancer Center

STUDY ASSESSMENTS 6.

The Prometheus system will be used as the database for data collection and query handling. This database system was developed at MD Anderson for conduction of phase II and phase III clinical trials. The investigator will ensure that data are recorded in the database as specified in the study protocol and in accordance with the instructions provided.

The investigator ensures the accuracy, completeness, and timeliness of the data recorded and of the provision of answers to data queries according to the Clinical Study Agreement.

6.1. **Demographics**

The demographics (date of birth, sex and race) details for each patient will be collected at the screening visit.

6.2. **Medical History**

The investigator should document all relevant and clinically significant medical conditions and illnesses that the patient has experienced at time of screening as medical history. Medical history should include treatment detailed information on all therapy directed against recurrent/metastatic HPV associated disease e.g., past surgical and/or radiation regimens. Any prior chemotherapy or immunotherapies, adjuvants, etc. should be recorded in the electronic medical record.

Illnesses first occurring or detected after the first protocol specific intervention or during the study and/or worsening of an existing illness in severity, frequency or nature after the signing of ICF are to be documented as AEs in the database.

6.3. **Efficacy Assessments**

RECIST v1.1 will be used to assess patient response to treatment by determining ORR, Disease Control Rate at 24 weeks (DCR-24w), and PFS. Objective response rate will also be assessed using immune-related RECIST (irRECIST). OS will also be evaluated.

The methods of assessment of tumor burden used at baseline are CT and/or MRI scans, preferably with IV contrast imaging, of the chest, abdomen, and pelvis. Any other areas of disease involvement should be additionally imaged based on the signs and symptoms of individual patients.

Radiologists at the MD Anderson Cancer Center have developed a multimedia structured reporting system, called ViSion, which will be used to capture the key images and metrics recorded by a radiologist for tumor response assessment. The captured images are tagged by a radiologist with metadata referenced to the SNOMED-CT ontology to indicate the anatomical location and radiological observation/diagnosis of each finding. The ViSion system displays serial image findings linked in graphical disease timelines. Target and non-target lesions may be designated by a radiologist from which the calculation and display of disease response criteria (e.g., RECIST) is automated. The radiologist's actual image analysis is performed using the institution's FDA-cleared Philips iSite picture archiving and communications system (PACS) display that is enabled with electronic calipers – ViSion only captures the annotated key images and metrics for subsequent storage, analysis and display. The ViSion database is housed within the

Version Number: 1.8 Date: July 26, 2019 Proprietary of MD Anderson Cancer Center

institutional firewall on an MD Anderson server, and the system is HIPAA-compliant requiring institutional passwords for controlled access.

The baseline assessment should be performed no more than 28 days before the start of MEDI0457 treatment and ideally as close as possible and not later than the start of the IP. Efficacy for all patients will be assessed by disease status assessments every 8 weeks (\pm 3 days) (relative to the date of the first MEDI0457 administration) for 1 year, if CR/partial response (PR)/SD are achieved then disease status assessments should be performed every 12 weeks (± 7 days) until the end of treatment. Disease status assessments will be performed once at the end of treatment if PD is observed, otherwise at end of treatment and then at Day 90 ± 3 days, every 3 months after Day 90 up to Month 12 ± 7 days then every 6 months after Month 12 ± 14 days until the end of study. If an unscheduled assessment is performed, and the patient has not progressed, every attempt should be made to perform the subsequent assessments at their scheduled visits (± 14 days).

For patients who discontinue therapy due to toxicity in the absence of confirmed objective progression, disease status assessments should be continued until confirmed PD or start of subsequent anticancer therapy.

Patients who discontinued from treatment for reasons other than PD will continue disease assessments until confirmed PD or start of subsequent anticancer therapy.

The response to immunotherapy may differ from the typical responses observed with cytotoxic chemotherapy including the following:

- Response to immunotherapy may be delayed,
- Response to immunotherapy may occur after PD by conventional criteria,
- The appearance of new lesions may not represent PD with immunotherapy, and/or
- SD while on immunotherapy may be durable and represent clinical benefit.

Based on the above-described unique response to immunotherapy and based on guidelines from regulatory agencies, e.g., European Medicines Agency's "Guideline on the evaluation of anticancer medicinal products in man" (EMA/CHMP/205/95/Rev.4) for immune modulating anticancer compounds, this study will include the following in addition to standard RECIST 1.1 criteria:

- RECIST will be modified so that PD must be confirmed with a second radiologic assessment, preferably, 5 weeks (+/- 7 days) after the initial assessment of PD in the absence of clinically significant deterioration. Treatment with study regimen should continue between the initial assessment of progression and confirmation for progression at outlined in Tables 4.
- In addition, subjects may continue to receive the study regimen beyond confirmed PD in the absence of clinically significant deterioration and if investigators consider that subjects may be deriving benefit from treatment and there are no more suitable alternative treatments available for the subject.

Version Number: 1.8

Proprietary of MD Anderson Cancer Center Date: July 26, 2019

Modification of RECIST as described is meant to discourage the early discontinuation of the study regimen and provide a more complete evaluation of its anti-tumor activity than would be seen with conventional response criteria. Nonetheless, the efficacy analysis will be conducted by programmatically deriving each efficacy endpoint based on the first evidence of progression (by modified RECIST 1.1 criteria described below) when progression is confirmed by a second scan.

Of note, clinically significant deterioration is considered to be a rapid tumor progression that necessitates treatment with anti-cancer therapy other than the study regimen or other symptomatic progression that requires urgent medical intervention (e.g., central nervous system metastasis, respiratory failure due to increasing malignant pleural effusion, or development of mechanical bowel obstruction due to carcinomatosis or tumor compression)

6.4. **HPV-16 or HPV-18 Testing**

Patients will be enrolled into the study based on a fresh or historical sample that has been tested and is positive for HPV-16 or HPV-18 positive by the institutionally approved assay. Please refer to section 6.6.1 for details regarding tissue collection.

6.5. **Safety Assessments**

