3.5. Criteria for Withdrawal

A patient will be considered to have completed the study when he/she completes all protocol specified scheduled study visits. The follow-up visit will be the last study visit.

If a patient discontinues or is withdrawn at any time after initiation of study treatment, the investigator should make every effort to have the patient complete all assessments designated for the follow-up visit. The investigator will make every effort to have all scheduled assessment blood samples collected as indicated in **Table 3**. Any AEs present at the time of discontinuation/withdrawal should be followed in accordance with the safety requirements outlined in Section 7.

Patients who discontinue study treatment will be followed for: (1) up to 90 days after last study treatment with durvalumab and/or MEDI0457; (2) until AE/SAE resolution or an outcome is reached for all events (see Section 7.4.2); or (3) until patient initiates alternative anticancer therapy. Patients who leave the study because of a serious or significant safety issues should be followed closely until the AEs are fully and permanently resolved or stabilized (if complete resolution is not anticipated), with the follow-up data recorded in the database (see Section 7.4.2 for further details regarding the follow-up of unresolved AEs).

If a patient discontinues from treatment for reasons other than disease progression, and therefore continues to have tumor assessments, drug or procedure-related SAEs must be captured until the patient is considered to have confirmed PD and will have no further tumor assessments.

Investigator should discuss the reason for any discontinuation of study treatment with the MDACC IND Office Medical Monitor prior to any action or within 24 hours when information becomes available.

The primary reason for the patient discontinuing study treatments or withdrawal from the study should be among the following standard categories.

• Adverse Event: Clinical or laboratory events occurred that, in the medical judgment of the investigator for the best interest of the patient, are grounds for discontinuation. This includes serious and non-serious AEs regardless of relation to study treatment.

Version Number: 1.8
Date: July 26, 2019

Proprietary of MD Anderson Cancer Center

• Death.

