- A persistent or significant incapacity or substantial disruption of the ability to conduct normal life functions.
- A congenital anomaly/birth defect.

Important medical events that may not result in death, be life-threatening, or require hospitalization may be considered a serious adverse drug experience when, based upon appropriate medical judgment, they may jeopardize the patient or subject and may require medical or surgical intervention to prevent one of the outcomes listed in this definition. Examples of such medical events include allergic bronchospasm requiring intensive treatment in an emergency room or at home, blood dyscrasias or convulsions that do not result in inpatient hospitalization, or the development of drug dependency or drug abuse (21 CFR 312.32).

Version Number: 1.8

Proprietary of MD Anderson Cancer Center Date: July 26, 2019

- 1. Important medical events as defined above, may also be considered serious adverse events. Any important medical event can and should be reported as an SAE if deemed appropriate by the Principal Investigator or the MDACC IND Office.
- 2. All events occurring during the conduct of a protocol and meeting the definition of a SAE must be reported to the IRB in accordance with the timeframes and procedures outlined in "The University of Texas M. D. Anderson Cancer Center Institutional Review Board Policy for Investigators on Reporting Serious Unanticipated Adverse Events for Drugs and Devices". Unless stated otherwise in the protocol, all SAEs, expected or unexpected, must be reported to the IND Office, regardless of attribution (within 5 working days of knowledge of the event).
- 3. All life-threatening or fatal events, that are unexpected, and related to the study drug, must have a written report submitted within 24 hours (next working day) of knowledge of the event to the Safety Project Manager in the IND Office.
- 4. Unless otherwise noted, the electronic SAE application (eSAE) will be utilized for safety reporting to the IND Office and MDACC IRB.
- 5. Serious adverse events will be captured from the time of the first protocol-specific intervention, until 90 days after the last dose of drug, unless the participant withdraws consent. Serious adverse events must be followed until clinical recovery is complete and laboratory tests have returned to baseline, progression of the event has stabilized, or there has been acceptable resolution of the event.

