- 6. Additionally, any serious adverse events that occur after the 90-day time period that are related to the study treatment must be reported to the IND Office. This may include the development of a secondary malignancy.

7.3. **Assessment of Safety Parameters**

7.3.1. **Severity**

Assessment of severity is one of the responsibilities of the investigator in the evaluation of AEs and SAEs. Severity will be graded according to the NCI CTCAE v4.03. The determination of severity for all other events not listed in the CTCAE should be made by the investigator based upon medical judgment and the severity categories of Grade 1 to 5 as defined below.

- Grade 1 (mild): An event that is usually transient and may require only minimal treatment or therapeutic intervention. The event does not generally interfere with usual activities of daily living.
- Grade 2 (moderate): An event that is usually alleviated with additional specific therapeutic intervention. The event interferes with usual activities of daily living, causing discomfort but poses no significant or permanent risk of harm to the subject.
- Grade 3 (severe): An event that requires intensive therapeutic intervention. The event interrupts usual activities of daily living, or significantly affects the clinical status of the subject.

Version Number: 1.8 Date: July 26, 2019 Proprietary of MD Anderson Cancer Center

• Grade 4 (life threatening): An event, and/or its immediate sequelae, that is associated with an imminent risk of death or with physical or mental disabilities that affect or limit the ability of the subject to perform activities of daily living (eating, ambulation, toileting, etc.).

• Grade 5 (fatal): Death (loss of life) as a result of an event.

It is important to distinguish between serious criteria and severity of an AE. Severity is a measure of intensity whereas seriousness is defined by the criteria in Section 10.1. A Grade 3 AE need not necessarily be considered an SAE. For example, a Grade 3 headache that persists for several hours may not meet the regulatory definition of an SAE and would be considered a nonserious event, whereas a Grade 2 seizure resulting in a hospital admission would be considered an SAE.

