7.4.1. Study recording period and follow-up for AEs and SAEs

AEs and SAES will be recorded from time of first protocol-specific intervention throughout the treatment period and including the follow-up period (90 days after the last dose of Durvalumab and/or MEDI0457). For physical exams, only abnormal findings will be recorded.

During the course of the study all AEs and SAEs should be proactively followed up for each subject. Every effort should be made to obtain a resolution for all events, even if the events continue after discontinuation/study completion.

If a subject discontinues from treatment for reasons other than disease progression, and therefore continues to have tumor assessments, drug or procedure-related SAEs must be captured until the patient is considered to have confirmed PD and will have no further tumor assessments.

The investigator is responsible for following all SAEs until resolution, until the subject returns to baseline status, or until the condition has stabilized with the expectation that it will remain chronic, even if this extends beyond study participation.

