7.4.2. Follow-up of unresolved adverse events

Any AEs that are unresolved at the subject's last visit in the study are followed up by the investigator for as long as medically indicated, but without further recording in the case report form. After 90 days, only subjects with ongoing IP-related SAEs will continue to be followed for safety.

AstraZeneca retains the right to request additional information for any subject with ongoing AE(s)/SAE(s) at the end of the study, if judged necessary.

Version Number: 1.8 Date: July 26, 2019

Proprietary of MD Anderson Cancer Center

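### AEs must be captured to 90 days after the last dose, but Table 3 schedules no AE assessment after end of treatment and Section 3.5 can be read as ending follow-up at new therapy, so late AEs may be under-ascertained

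*Combined protocol and SAP*

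**What the plan says.** **The recording rule.** Section 7.4.1 has AEs and SAEs recorded from the first protocol-specific intervention through treatment, "including the follow-up period (90 days after the last dose of Durvalumab and/or MEDI0457". For SAEs, Section 7.2 sets the window "until 90 days after the last dose of drug, unless the participant withdraws consent", so withdrawal of consent is the only stated exception. It adds that "any serious adverse events that occur after the 90-day time period that are related to the study treatment must be reported to the IND Office".

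**The schedule.** Section 5 makes Table 3 govern all study procedures. The row "Adverse events assessment" is marked at every column from Screening to EOT and is blank under Follow-up. Note b defines EOT as the visit at which stopping is decided. Note c states "A clinic visit is not required for follow-up" and provides a six-monthly vital-status check, by phone or record, for patients taken off study for progression or intolerable toxicity.

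**The end of follow-up.** Section 3.5 lists three endpoints for patients who discontinue treatment: up to 90 days, AE/SAE resolution or outcome, or "3) until patient initiates alternative anticancer therapy".

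**The follow-up visit.** Note e of Table 3 calls for "Complete physical examination during Screening and at the Follow-up visit". Section 6.5.4 repeats this, 6.5.5 places an ECOG assessment at follow-up, and 3.5 asks for completion of the assessments designated for that visit.

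**Unresolved events.** Section 7.4.2 has AEs unresolved at the last visit followed "without further recording in the case report form". Section 3.5 wants follow-up data in the database for patients who leave because of a serious or significant safety issue.

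**The concern.** A recording rule works only if the site has a way to learn of events. Sections 7.2 and 7.4.1 set the 90-day duty but name no contact at which AEs are asked about. Reporting clocks start at knowledge of the event (7.2 for SAEs, 7.5 for AEs of special interest), and Table 3 gives no planned way to gain that knowledge after EOT.

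Safety of the combination is the first secondary objective listed in Section 2.2. Section 8.3.2 summarizes it as the percentage of patients with AEs, by grade and attribution. An event that is never elicited counts as no event, so incomplete ascertainment can only lower that percentage. Section 1.3.1 says the combination is being studied for the first time in these patients, and Section 1.4 accepts a risk of additive or synergistic toxicity. The protocol also uses 90 days after the last dose for contraception (3.3.2) and blood donation (3.3.3), so it treats that period as one of continuing relevance.

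**Working it through.** The plan gives no figure to reproduce here. The check is a reading of Table 3 against the text, followed by arithmetic on the 90-day window.

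**1. Table 3, row by row.** The table has 12 columns: Screening; Weeks 1, 3, 4, 7, 8, 10, 12, 16 and 20; EOT; Follow-up. The AE row has 11 marks, Screening to EOT, and the Follow-up cell is empty. The physical-examination and ECOG rows show the same pattern. The columns are not misaligned, because the disease-status row does carry a Follow-up mark. That mark is note k, which applies only if there is no progression. For a patient who stops for progression, the Follow-up column therefore schedules nothing.

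**2. The passages side by side.**

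| Question | One place | Another place |
|---|---|---|
| How long are AEs captured? | 90 days after last dose (7.2, 7.4.1) | Last scheduled AE assessment at EOT (Table 3) |
| Can new therapy end it earlier? | Not listed as an exception (7.2, for SAEs) | Listed as an end of follow-up (3.5) |
| Is there a follow-up visit? | Assumed (note e, 3.5, 6.5.4, 6.5.5) | Not required (note c) |
| Are unresolved AEs recorded after the last visit? | In the database, for those leaving over serious or significant safety issues (3.5); AEs recorded to 90 days for all (7.4.1) | Not in the case report form (7.4.2) |

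**3. Days with no scheduled AE assessment.** The window runs from the last dose and scheduled assessment ends at EOT. If EOT falls g days after the last dose, the uncovered part is 90 − g days. The documents do not fix g. The values below are assumptions based on the later dosing intervals in Section 4.4.1 (durvalumab every 4 weeks, MEDI0457 every 8 weeks).

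- g = 0 (EOT on the day of the last dose): 90 − 0 = 90 days; 90/90 = 100%.
- g = 28 (one durvalumab interval): 90 − 28 = 62 days; 62/90 = 69%.
- g = 56 (one MEDI0457 interval, if it alone continues): 90 − 56 = 34 days; 34/90 = 38%.

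A longer hold before EOT shrinks the gap further.

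**4. The next contact under note c.** Counted from about the last dose (an assumption, since the note gives no starting point), six months is about 183 days. That is 183 − 90 = 93 days after the window closes, and the contact asks only about vital status.

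**5. What cannot be computed.** The documents give no event rate after EOT, so neither the number of events lost nor the size of the downward bias can be derived.

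**The case against.** The strongest reply is that a blank cell does not cancel Section 7. Capture to Day 90 is mandatory in two places, and related SAEs stay reportable after that. Section 7.4.1 asks for proactive follow-up of every event, and 3.5 asks for every effort to complete the follow-up assessments. A reader might infer that late toxicity is simply missed. The documents do not support that; a careful site could collect everything. What remains is that none of these passages schedules a contact.

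A reader might also infer that 3.5 waives the 90-day rule once new therapy starts. It does not say so. Three items are joined by an or, with no statement of which governs, and the preceding paragraph sends AEs present at discontinuation to Section 7. It is an ambiguity, though one that a site could reasonably resolve by stopping early.

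Note c speaks of patients taken off study, whereas 3.5 speaks of those who discontinue treatment and follows them up to 90 days. The six-month check is therefore not necessarily the first contact of any kind. It is the only one that Table 3 names for patients who have progressed.

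Patients who stop without progression are less exposed. Note k and Section 6.3 give them a disease assessment at Day 90, and 3.5 and 7.4.1 continue capture of drug- or procedure-related SAEs until confirmed progression. This stands, but it does not cover their non-serious events.

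Finally, one could argue that about half of the intended AE time is uncovered, for example 13 of 12 + 13 = 25 weeks for a patient treated for 12 weeks. That assumes EOT on the day of the last dose and a treatment length the plan does not state. Section 3.4 also requires progression to be confirmed at least 4 weeks later, and under 6.3 treatment normally continues meanwhile. Share of time is in any case not share of events.

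**Conclusion.** The concern holds as an internal inconsistency with a plausible effect on a secondary objective. Followed as written, Table 3, note c and 3.5 leave patients who progress with no scheduled AE ascertainment for part or all of the window that 7.2 and 7.4.1 mandate: between 34 and 90 of the 90 days if EOT comes 0 to 56 days after the last dose. Late AEs may therefore be under-ascertained, above all non-serious ones and those in patients who progress and switch therapy. The direction of any bias in the percentage of patients with AEs is downward. Its size is unknown.

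The effect stops there. The primary ORR does not depend on AE collection. The DLT stopping rule uses the 4 weeks after the first durvalumab dose (6.7.2), when Table 3 still schedules AE assessments for patients on treatment. The conflict between 3.5 and 7.4.2 on unresolved events is narrower and secondary, because 3.5 speaks only of patients leaving over serious or significant safety issues and itself refers to 7.4.2.

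**What to change.** - **Table 3, Follow-up column.** Add a review of AEs, concomitant medication and subsequent therapy, by phone or chart, at about Day 90 after the last dose of either drug, for all patients whatever the reason for stopping. Combine it with the Day 90 scan where there is one. Note k counts that scan from EOT: with EOT 28 days after the last dose it falls at 28 + 90 = 118 days after the last dose. The review should therefore record onset dates and cover the whole window. An earlier contact, for example at Day 30, is optional.
- **Section 3.5.** State that new anticancer therapy does not end AE/SAE recording before Day 90. Record the start date of that therapy, so that events before and after it can be tabulated separately.
- **Follow-up visit.** Reconcile note c with note e, 3.5, 6.5.4 and 6.5.5 on whether a visit takes place, and make the Table 3 cells for examination and ECOG agree with the answer.
- **Unresolved AEs.** Make 3.5, 7.4.1 and 7.4.2 agree on what is recorded after the last visit.

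The cost is one or two brief contacts per patient and some redrafting. The AE review itself needs no extra clinic visit. The drawback is that some recorded AEs will belong to the next therapy, which the recorded start date allows the analysis to show.
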